Hypothesis: The use of a novel adherence intervention (the AdhereTech bottle with reminders) will improve adherence to HIV medications over 12 weeks.

Primary Objective: To assess adherence to a tenofovir-based regimen over 12 weeks in patients using the AdhereTech bottle with reminders compared to the usual standard of care.

Primary Endpoint: The mean change in drug levels of tenofovir diphosphate (TFV-DP) in red blood cells using dried blood spots between week 0 and week 12 in the AdhereTech intervention group compared with the standard of care group.

Secondary Objectives:

- 1) To assess the feasibility of using the AdhereTech bottles with phone/text reminders in HIV-infected patients.
- 2) To assess the use of tenofovir diphosphate dried blood spots as a marker of HIV medication adherence in comparison with plasma tenofovir levels and self-reported medication adherence.

Secondary Endpoints:

- 1) The percentage of patients completing the 12 week AdhereTech intervention in comparison with the standard of care group.
- 2.1) Compare the mean change in TFV-DP blood spot level, TFV plasma level, and self-reported medication adherence between weeks 0 and 12 in the AdhereTech intervention and standard of care groups.
- 2.2) The mean change in HIV level and percent of patients with an HIV RNA below the level of detection between weeks 0 and 12 in the AdhereTech intervention and standard of care group.

RESEARCH PLAN:

Selection of Participants

Type of the Participant Population

This study is open to all adults who meet the following inclusion and exclusion criteria.

Inclusion and Exclusion Criteria:

Inclusion Criteria:

- Male and nonpregnant female subjects aged 18 years and older
- A diagnosis of HIV-1
- Undergoing therapy with a tenofovir-based antiretroviral regimen
- Suboptimal adherence to the tenofovir-containing HIV antiretroviral regimen over the prior 52 weeks from the time of enrollment, as evidenced by 2 HIV RNA levels above the level of

detection following an HIV RNA level below the level of detection, with no plans to change the current HIV drug regimen.

- Access to and willingness to use a cell phone to receive voice/text reminders to take HIV medications. Subjects must also agree to maintain a stable phone number and active cell phone service for the duration of the study.
- Adequate English to provide written, informed consent and to provide reliable responses to the study interview

Exclusion Criteria:

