At weeks 0 and 12, patients will undergo testing for dried blood spot tenofovir diphosphate (TFV-DP) level, HIV RNA level, CD4 cell count, and safety labs (complete metabolic panel, phosphorous, liver function testing, and complete blood count). Please see tables 1 and 2 for the schedule of assessments and treatment plan.

All patients will receive reimbursement in the form of a Metro card, which will cover the cost of two subway rides (value \$5.50, in addition to the card purchasing fee). The cards will be provided at each visit, except for the initial screening visit.

Schedule of Events:

The schedule of study events is included below.

Table 1 – Schedule of Assessments

Visit Day and Window	Screening (Day - 45 to Day -1)	Enrollment (week 0, Day 0)	week 4 (+/- 7 days)	week 8 (+/- 7 days)	week 12 (+/- 7 days)
Obtain informed consent	X				
Randomization		X			
History and physical exam	X				
AdhereTech bottle filled and dispensed		X	X	X	
Interval history		X	X	X	X
Routine adherence counseling		X			
Dried blood spot for TFV-DP level		X			X
Plasma for TFV level		X	X*	X*	X
Plasma HIV RNA level		X			X
Whole blood CD4 cell count		X			X
Plasma BMP, LFTs, and phosphorous		X			X
Adherence questionnaire by CASI		X	X	X	X

Abbreviations: *TFV-DP – tenofovir diphosphate, TFV – tenofovir, BMP – basic metabolic panel, LFTs – liver function tests*

*For the secondary analysis, plasma TFV levels will be analyzed from weeks 0 and 12. If additional funding is obtained, we will analyze replicate specimens at weeks 0 and 12 plus weeks 4 and 8.

Table 2 – Blood volumes

Bodily Fluid	Amount	Frequency	Total
Blood - Plasma TFV	6mL	Weeks 0, 4, 8, and 12	36ml
Blood – TFV-DP blood spot *	4mL	Weeks 0 and 12	12mL
Blood – HIV RNA	6 ml	Weeks 0 and 12	12mL
Blood – CBC and CD4 cell count	6mL	Week 0	6mL
Blood – BMP, phosphorous, LFTs	6ml	Weeks 0 and 12	12mL

Abbreviations: *TFV-DP – tenofovir diphosphate, TFV – tenofovir, CBC – complete blood count, BMP – basic metabolic panel, LFTs – liver function tests*

*All labs will be processed locally at Weill Cornell/NYPH. The TFV-DP dried blood spot and plasma TFV levels will be assayed by the Colorado Antiviral Pharmacology Laboratory at the University of Colorado Denver. Protocol is included in Appendix F.

HIV Therapy:

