In this pilot study, the sample size calculation is based on the null hypothesis of no difference in tenofovir-diphosphate (TFV-DP) concentrations (by dried blood spots) at baseline versus a demonstrable difference at week 12. From a simulation study (Castillo), we expect to see the same mean concentration (standard deviation) at both groups at baseline: 900 (404) fmol/punch. At 12 weeks, we expect to see a mean concentration (standard deviation) of 1332 (597) fmol/punch in arm A (adherence intervention) vs. 900 (404) fmol/punch in arm B (control). Assuming normal distribution of TFV-DP concentrations, type 1 error = 0.05, power = 80%, a sample size of 32 will be recruited per arm (64 total) based on a two-sided, two-sample t-test with equal variance. Since the data may have missing data at the last visit, we will add ~10% more participants. Therefore, the final sample size of 35 per arm (70 total) will be enrolled.

We intend to screen approximately 100 total subjects, as we assume there will be subjects who may sign the consent form, but ultimately do not participate in the study due to screen failure, not meeting inclusion/exclusion criteria, and personal choice.

Randomization will be provided by the biostatistician from Weill Cornell Medical College. The randomization list will be provided to the principal investigators.

Data Analysis:

For the primary analysis, we will compare the mean change in drug levels of tenofovir diphosphate (TFV-DP) in red blood cells using dried blood spots between week 0 and week 12 in the AdhereTech intervention group compared with the standard of care group via a two-sided t-test. If the data will not meet the normal assumption, non-parametric Wilcoxon Rank Sum test will be used to test medians between two groups.

For the secondary analyses, we will:

- Calculate the mean percentage of patients who complete the 12 week AdhereTech intervention and compare that with the percent that complete 12 weeks of follow-up in the standard of care group.
- Compare the mean change in TFV-DP blood spot level with TFV plasma level and self-reported medication adherence from weeks 0 and 12 between the AdhereTech intervention and standard of care groups.
- Compare the mean change in HIV level and median percent of patients with an HIV RNA below the level of detection from weeks 0 and 12 between the AdhereTech intervention and standard of care group.

These analyses will be performed via two-sided t-tests.

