U.S. Department of Health and Human Service, Guidelines for the Use of Antiretroviral Agents in HIV-1-Infected Adults and Adolescents, 2/12/13, available at www.aidsinfo.nih.gov

Watson A. Vitality GlowCaps Trials with Mass General Hospital and Harvard Center for Connected Health. 2008, available at <http://www.connected-health.org/events/past-events/symposium-2008/presentations.aspx>

Protocol Addendum (09-30-2016):

Addendum to Data Analysis Plan:

Due to enrollment being slower than anticipated as of August 2016 (40 of 70 total participants enrolled), we will perform an interim analysis of the tenofovir dried blood spot data for the primary endpoint. The statistician will be blinded to the participants' study group assignments. The statistician will notify us if there is a significant difference detected in the tenofovir dried blood spot levels between the two groups, but the study investigators will be blinded as to the detailed results. Such information will help us determine whether further enrollment into the study is justified. If the difference seen is $</= 5\%$ at the 5% level of significance, study enrollment will be terminated due to futility of the intervention. If the difference seen is $>/= 20\%$ at the 5% level of significance, the study will be terminated due to a significant difference demonstrating efficacy of the Intervention. If the difference is between 6-19%, study enrollment will continue as previously planned until the target sample size of 70 subjects is achieved.

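### The 80% power is derived for week-12 TFV-DP levels, but the primary test is an unadjusted t-test on change; ANCOVA on week-0 TFV-DP keeps the endpoint and gains precision at low to moderate correlation

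*Combined protocol and SAP*

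**What the plan says.** Under Study Objectives and Endpoints, the primary endpoint is "The mean change in drug levels of tenofovir diphosphate (TFV-DP) in red blood cells using dried blood spots" from week 0 to week 12, compared between arms. Under Data Analysis, the intervention arm's mean change is "compared with the standard of care group via a two-sided t-test". No covariate is named. If normality fails, a "non-parametric Wilcoxon Rank Sum test will be used to test medians between two groups", again without adjustment.

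The Sample Size Estimate works on levels. Both arms are expected to be at 900 (404) fmol/punch at baseline. "At 12 weeks, we expect to see a mean concentration (standard deviation) of 1332 (597) fmol/punch in arm A", against 900 (404) in arm B. The 32 per arm is "based on a two-sided, two-sample t-test with equal variance", at two-sided 5% and 80% power. About 10% is then added, giving 35 per arm, for this reason: "Since the data may have missing data at the last visit".

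Under Study Visits: "At weeks 0 and 12, patients will undergo testing for dried blood spot tenofovir diphosphate (TFV-DP) level". The baseline value is therefore scheduled for every patient. Neither the main text nor the 2016 addendum gives an SD of change, a within-patient correlation or a baseline-adjusted analysis.

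**The concern.** The quantity that was powered is not the quantity that will be tested. Because the expected baselines are equal, the target difference is 432 fmol/punch for levels and for change alike. The SD is not the same, and the SD of change depends on rho, which the plan never states. A reader cannot tell what power the primary test has.

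The SD behind the 32 is not stated either. The calculation assumes equal variance, while the plan lists 597 and 404.

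Subtraction also forces a coefficient of 1 on baseline. If rho is low to moderate, that adds baseline noise to the comparison, and a regression on the same data would remove it. Precision matters here: the addendum reports 40 of 70 enrolled, recruitment behind plan, and an interim look at the primary endpoint.

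**Working it through.** **Inputs.** From the Sample Size Estimate: difference 1332 − 900 = 432; baseline SD 404 in both arms; week-12 SDs 597 (A) and 404 (B); two-sided 5%. Rho is an assumption throughout and is taken to be the same in both arms.

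**1. The plan's own figure.** With SD 597 in both arms, the normal approximation gives 2 × (1.960 + 0.842)² × (597/432)² ≈ 30 per arm. The exact noncentral-t calculation gives 31 (80.0% power), and 81.3% at 32. With the two SDs pooled, √((597² + 404²)/2) = 509.7, the exact answer is 23 per arm, and power at 32 is 91.6%. Only SD 597 in both arms comes close to the stated 32.

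**2. SD of change.** For each arm the variance is s₀² + s₁₂² − 2ρs₀s₁₂.

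- ρ = 0: A √(404² + 597²) = 720.9; B 404√2 = 571.3; pooled 650.
- ρ = 0.3: A √(519,625 − 144,713) = 612.3; B 404√1.4 = 478.0; pooled 549.
- ρ = 0.2 and 0.5: pooled 585 and 470.

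Put into the noncentral t at 32 per arm, these give 74.4, 82.8, 87.2 and 95.2% at ρ = 0, 0.2, 0.3 and 0.5. Power reaches 80% at ρ ≈ 0.13 (32 per arm), 0.05 (35) and 0.49 (20). With week-12 SD 597 in both arms, the thresholds are about 0.31, 0.24 and 0.61.

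**3. Why ANCOVA keeps the endpoint.** If week 12 = a + τ·arm + b·week 0, then change = a + τ·arm + (b − 1)·week 0, with the same τ and the same residuals. In one simulated data set both fits gave an estimate of 256.85 with HC3 standard error 136.13. The change t-test amounts to fixing b = 1. With the plan's SDs the average slope is ρ × 500.5/404 ≈ 1.24ρ, which reaches 1 only near ρ = 0.8.

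**4. Power, HC3 ANCOVA against change t-test (%).** ANCOVA by simulation: normal data, 60,000 trials per cell, t with 2n − 3 df.

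| Setting | ρ = 0 | 0.2 | 0.3 | 0.5 |
|---|---|---|---|---|
| 32 per arm, plan SDs | 90 v 74 | 91 v 83 | 92-93 v 87 | 96 v 95 |
| 35 per arm, plan SDs, none missing | 93 v 78 | 94 v 86 | 95 v 90 | 98 v 97 |
| 20 per arm, plan SDs | 70 v 53-54 | 72 v 62 | 74 v 68 | 82 v 81 |
| 32 per arm, week-12 SD 597 in both | 79 v 66 | 81 v 74 | 83 v 79 | 90 v 90 |
| 20 per arm, week-12 SD 597 in both | 56 v 45 | 59 v 54 | 60 v 58 | 69 v 71 |

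The 20-per-arm rows assume that the 40 enrolled split equally and all have both samples.

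Mean 95% CI half-width at 32 per arm with the plan's SDs: 262 v 324, 257 v 291, 250 v 273 and 228 v 234 fmol/punch.

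At higher rho and 20 per arm, HC3 ANCOVA falls below the change test: by about 1 point at ρ = 0.6 and 0.7 with the plan's SDs, and by about 3 points with SD 597 in both arms.

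**5. Type I error** (ρ = 0.3, equal means, SDs 597 and 404). With 32 per arm, HC3 gives 4.5% and model-based ANCOVA 5.0%. With 28 measured in the SD-597 arm against 35 in the other, HC3 gives 4.7%, model-based ANCOVA 6.2% and the change t-test 5.5%.

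**6. Skewed data.** With lognormal data at the plan's means and SDs and 32 per arm, HC3 ANCOVA against the change t-test is 91.9 v 75.2, 93.8 v 87.3 and 96.8 v 95.2% at ρ = 0, 0.3 and 0.5.

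**The case against.** The planned test is valid, and endpoint and test agree with each other. Only one nuisance parameter is missing, in a self-described pilot, and 35 measured per arm would give 78% even at ρ = 0. **This stands**: it is why the point is about checkability and efficiency and not about an error in inference.

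The gain depends on an assumed rho. **This also stands.** TFV-DP's long half-life might suggest a high rho. But the background section gives 17 days, so 84 days is about 4.9 half-lives and about 3% of week-0 drug remains. Correlation would have to come from stable differences between patients. That does not establish rho in either direction.

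HC3 costs some power, and a Welch test on change would be a smaller edit that also handles unequal variances (type I error 5.1% with 28 against 35 measured). This is true, but Welch recovers none of the precision lost by subtraction. Model-based ANCOVA avoids HC3's power cost (72.1% against 69.2% at 20 per arm, SD 597, ρ = 0.5), but it exceeds 5% when the arms become unbalanced.

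The plan's SDs are proportional to its means (404/900 and 597/1332 are both about 0.45), so skew is possible, and the fix moves the rank-sum test from fallback to sensitivity analysis. That is a real change to the plan and must be stated. It does not cost power in practice. With lognormal data at 20 and 32 per arm, HC3 ANCOVA was ahead of the rank-sum test on change by about 6 to 20 points at ρ = 0 to 0.3 and by 1 to 2 at 0.5, and within about 1 point at 0.7.

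Finally, 40 enrolled is not 40 with week-12 samples, so the 20-per-arm figures are illustrative only.

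**Conclusion.** The concern holds. The stated 80% belongs to a comparison of week-12 levels with an unstated SD, apparently 597 in both arms, and not to the planned test of change.

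With the plan's SDs at 32 per arm, baseline adjustment adds about 16 points of power at ρ = 0, 8 to 9 at 0.2, 5 at 0.3 and 1 at 0.5. With SD 597 in both arms the gain is about 14, 7, 3 and nil. The worst loss found is about 3 points, at 20 per arm with ρ of 0.6 to 0.7 and SD 597 in both arms.

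These figures rest on the plan's means and SDs, an assumed rho common to both arms, and normal data with a lognormal check. They do not show that the trial is underpowered or that the t-test is wrong. The change should be made because the possible gain is large relative to its cost.

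**What to change.** - Make the primary analysis an ANCOVA of change in TFV-DP on arm and week-0 TFV-DP, on the original scale, with HC3 standard errors. Report the adjusted difference in mean change (fmol/punch) with its 95% CI.
- Report unadjusted mean change by arm alongside. Keep the rank-sum test on change as a sensitivity analysis, and say that this replaces its present role as fallback.
- Restate the sample-size paragraph as based on week-12 levels. Give the SD used and an assumed rho with a range, and say that the figure is only approximately a lower bound for the ANCOVA.

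**Cost.** Wording, one degree of freedom and a small HC3 penalty; no new data, and the endpoint and its units are unchanged. At ρ = 0 the ANCOVA is 1 to 4 points below a t-test on week-12 levels: 90 against 91-92% at 32 per arm and 70 against 74% at 20 per arm with the plan's SDs, and 79 against 81% at 32 per arm with SD 597 in both arms. The loss at high rho is as given above.

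**Timing.** The change must be dated before any by-arm TFV-DP comparison is seen, including the addendum's interim analysis. If that has already happened, the ANCOVA can only be supportive and the planned t-test stays primary.

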AdhereTech has created patented smart pill bottles that improve medication adherence. These bottles automatically measure the number of pills in the bottle in real-time, and wirelessly transmit this HIPAA-compliant data to a central server. If a patient hasn't taken his/her medication, the technology is able to remind them via phone call or text message. The AdhereTech bottle also has on-bottle lights and chimes that are automatically triggered to remind patients to stay adherent. When patients receive reminders the via a phone call, patients can leave feedback and information as to the main reason why they didn't take a dose (e.g., side effects, lack of information, lack of symptoms, or any other issues.) Patients use the AdhereTech bottles in the same way they use normal pill bottles. The bottles have a cell phone chip build inside, so they can work anywhere as they collect and send adherence data. The bottles never need to be charged or kept in a particular location, so patients can travel with the bottles. Thus, little, if any behavior change is needed to effectively use this adherence-promoting device.

[figure not shown]
Tenofovir disoproxil fumarate (TDF, trade name: Viread) is a nucleoside analogue that is a preferred first-line drug in current HIV treatment guidelines (DHHS). TDF is used commonly as part of 3 available one-pill, once-daily combination HIV drug regimens: TDF + emtricitabine + efavirenz (Atripla), TDF + emtricitabine + rilpivirine (Complera), and TDF + emtricitabine + elvitegravir + cobicistat (Stribild), and is used commonly in other HIV regimens. TDF is phosphorylated intracellularly to tenofovir diphosphate (TFV-DP), a compound with a long half-life of 17 days in cells; the measurement of TFV-DP drug levels in dried blood spots recently was shown to estimate average drug exposure over 12 weeks (Castillo-Mancilla). This longer term measure of adherence can be compared with plasma tenofovir levels that estimate short-term adherence over 1-3 days.

We propose to conduct a randomized, pilot study of the novel adherence intervention, AdhereTech bottles with reminders, in HIV-infected patients with documented suboptimal adherence to their TDF-containing antiretroviral regimen.

STUDY SCHEMA:

See below

HABIT

Abbreviations: TDF – tenofovir disproxil fumarate, TFV-DP - tenofovir diphosphate (TFV-DP), TFV – tenofovir 4

STUDY OBJECTIVES AND ENDPOINTS:

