The ongoing choice of a patient's HIV antiretroviral regimen will be at the discretion of his/her primary provider, who will not be involved directly in this study. In all circumstances, the health and welfare of the patient will take precedence over study participation and as such, they will be provided with sufficient information about alternative treatments that may be offered outside of the study. If a patient's treating provider decides that s/he should no longer be on a tenofovir-based regimen during the course of the study, the reason for this change will be recorded, the adherence intervention will be discontinued, and the patient will remain in the study for the purpose of an intention-to-treat analysis.

Early Withdrawal:

Any patient who wishes to withdraw from the study is able to do so at any stage. These patients will be encouraged to attend a follow-up visit prior to withdrawal in order to discuss reasons for withdrawal, as well as any safety issues that may be relevant. At this visit a follow-up questionnaire and blood samples will be collected (as per a normal follow-up visit).

Discontinuing a Patient:

Patients will be discontinued from the study if, at any time, they are considered by the study investigators to be unlikely to participate in the necessary follow-up (i.e. due to an inpatient hospital admission, change of residence, incarceration, or a severe medical/psychiatric illness that precludes the patient's ability to make clinic visits or comprehend study procedures) and/or if the patient becomes unwilling to provider blood samples while on the study. In such cases, the adherence intervention will be discontinued and the patient will remain in the study for the purpose of an intention-to-treat analysis.

Duration/Length of follow-up:

Each patient will be followed for a total of 12 weeks after enrollment.

STATISTICAL CONSIDERATIONS AND DATA ANALYSIS PLAN:

Sample Size Estimate:

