Initial analysis will be performed based on an intent-to-treat basis. An additional secondary per-protocol analysis will also be performed, including only those patients who completed the intervention originally allocated and excluding patients who discontinued the AdhereTech study intervention early for reasons clearly not related to the intervention (i.e. HIV regimen changed by primary provider, imprisonment, or relocation).

HUMAN SUBJECTS CONCERNS:

Recruitment:

Recruitment will occur via various means. First, physicians and nurse practitioners caring for people with HIV within the Weill Cornell Center for Special Studies and Primary Care clinics will be notified of the study and asked to identify potentially eligible patients who meet the inclusion criteria from a review of their case records. These providers: (1) will ask potential participants: if they are interested in participating in the study, and if so, to call one of the investigators, or the research coordinators, or (2) will identify patients who would be suitable for the study and contact the patients via mail. He/she will mail a letter and a study flyer describing the study to the patients inviting them to call the research team for more information. Samples of the letter and study flyer are provided in Appendices G-J. Patients will be approached only by their clinical care providers and not by any members of the research team. Second, the IRB-approved recruitment fliers will be posted in the Weill Cornell Center for Special Studies and Primary Care clinics. Third, potential participants will be identified via current use of tenofovir and this protocol's inclusion/exclusion criteria by a search of Weill Cornell/NYPH medical records. Potential study participants will be

approached for participation in this study only by their primary medical providers and not by the study investigators. Prior to obtaining informed consent, potential participants will be screened for eligibility according to the inclusion and exclusion criteria specified. Once it is determined that participants meet these criteria and have provided informed consent, additional screening as specified in the Study Time Line will be conducted between weeks -2 and 0.

Consent Process:

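### The feasibility comparison uses a different completion event in each arm, and Objective 2 has no analysis relating the adherence markers within patients; per-protocol completion also needs a definition in the control arm.

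*Combined protocol and SAP*

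**What the plan says.** **Feasibility.** Secondary Objective 1 is "To assess the feasibility of using the AdhereTech bottles with phone/text reminders in HIV-infected patients". Its endpoint is "The percentage of patients completing the 12 week AdhereTech intervention in comparison with the standard of care group", which names no event for the control arm. The Data Analysis section supplies one: it calculates completion of the AdhereTech intervention and will "compare that with the percent that complete 12 weeks of follow-up in the standard of care group". The method for all secondary analyses is a two-sided t-test. Under HIV Therapy, if the provider takes a patient off tenofovir, "the adherence intervention will be discontinued, and the patient will remain in the study for the purpose of an intention-to-treat analysis".

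**Markers.** Secondary Objective 2 is "To assess the use of tenofovir diphosphate dried blood spots as a marker of HIV medication adherence in comparison with plasma tenofovir levels" and self-reported adherence. Endpoint 2.1 and the matching Data Analysis item give mean changes from week 0 to week 12 in the two arms, again by t-test. No correlation, agreement or regression analysis of the markers appears anywhere in the document.

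**Per-protocol set.** This is described as "including only those patients who completed the intervention originally allocated and excluding patients who discontinued the AdhereTech study intervention early", with the exclusion limited to reasons clearly unrelated to the intervention (regimen change, imprisonment and relocation are the examples). Completion is not defined.

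**The concern.** A two-arm comparison of completion is informative only if success means the same thing in both arms. Here, a patient who attends every visit but has stopped the bottle is a failure in the AdhereTech arm, while a control with the same attendance is a success. A significant difference could therefore come from retention, from bottle stopping or from both, and the test cannot separate them. Bottle stopping is a genuine feasibility outcome, but it has no control-arm counterpart.

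For Objective 2, an arm effect on each marker says nothing about whether patients with high TFV-DP also have high plasma tenofovir or report good adherence. The objective would be only partly answered.

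The per-protocol point is smaller. For controls, the allocated intervention is usual care with counseling, which Table 1 marks at week 0 only, so completing it has no stated meaning.

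**Working it through.** The plan gives no completion rate, stopping rate or expected correlation, so there is no figure of its own to reproduce on this point. The inputs taken from it are 35 per arm, 64 patients in total before the roughly 10% allowance for missing data, 40 enrolled when the Addendum was written, and the planned week-12 difference and larger SD (432 and 597 fmol/punch). All other rates are assumptions.

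**1. Feasibility comparison.** Let R be retention to week 12, equal in both arms, and s the share of retained AdhereTech patients who stop the bottle. Completing the intervention is taken to require staying to week 12. The control proportion is then R, the AdhereTech proportion is R(1 − s), and the gap is R × s although retention is identical. Because s cannot be negative, the expected AdhereTech figure can only be lowered.

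The rejection probability is exact: sum Binomial(a; 35, R(1 − s)) × Binomial(b; 35, R) over all pairs of counts (a, b) for which the pooled two-sided t-test on the 0/1 data (68 df) has p < 0.05.

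| s | AdhereTech proportion, R = 90% | Gap, points | Rejects |
|---|---|---|---|
| 0 | 90.0% | 0 | 5.7% |
| 3% | 87.3% | 2.7 | 7.2% |
| 5% | 85.5% | 4.5 | 9.5% |
| 10% | 81.0% | 9.0 | 19% |
| 20% | 72.0% | 18.0 | 49% |

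For s = 0, 5%, 10% and 20%, the rates are 4.9%, 6.6%, 12% and 32% with R = 80%, and 3.6%, 12%, 29% and 67% with R = 95%. The pattern does not depend on the choice of 90%.

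**2. Objective 2.** Suppose both markers show an arm effect of 432/597 = 0.72 SD, with 35 per arm. In 5,000 simulated trials, the between-arm t-tests reject about 85% of the time whether the within-arm correlation of the markers is 0 or 0.8. The planned tests therefore carry no information about how the markers relate within patients.

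Adjustment for arm is needed after randomization. With the same arm effect, 32 per arm and a true within-arm correlation of zero, the pooled Spearman coefficient averages about 0.115, and the arm-adjusted one about 0.

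Precision of the missing analysis, for an observed correlation of 0.5 (z = atanh 0.5 = 0.549, SE = √[(1 + 0.5²/2)/(n − 3)]):
- n = 64: SE = √(1.125/61) = 0.136; z from 0.283 to 0.815; CI 0.28 to 0.67.
- n = 36 (40 enrolled less about 10%): SE = √(1.125/33) = 0.185; z from 0.187 to 0.911; CI 0.19 to 0.72.

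Adjusting for arm (n − 4 in place of n − 3) barely changes these limits.

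**3. Per-protocol set.** No arithmetic applies. The first clause, on completing the allocated intervention, covers both arms but has no criterion. The second names only AdhereTech discontinuations, although regimen change, imprisonment and relocation can occur in either arm.

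**The case against.** **Stopping the bottle while staying in follow-up may be rare.** The only route that the protocol describes clearly is a switch off tenofovir, and patients must enter "with no plans to change the current HIV drug regimen". The Discontinuing a Patient section concerns people judged unlikely to attend follow-up. This stands as a limit on size: at 3% to 5% stopping, the rejection rate is 7% to 10%, not far above 6%. Informal abandonment of the bottle is possible, but no rate is given. A reader might expect a gap as large as 25/35 against 32/35. That needs 7 of 32 retained patients (22%) to stop, which nothing in the documents supports, and its significance depends on the test (t-test p = 0.03, Fisher p = 0.062).

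**These rejections are not type 1 errors in the strict sense.** That is correct. If patients stop the bottle, the two named proportions do differ. The fault lies in what the difference would be taken to mean. Nor could the mismatch produce a false claim for the bottle, since it works against it.

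**The plan may already intend a cross-marker comparison.** Its wording for the marker item leaves some room for that. But a t-test of mean change between arms, on measures in different units, does not relate them within patients. The planned tests remain valid for the arm effect on each marker.

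**The per-protocol wording might be read as favouring the bottle**, by keeping controls who come off tenofovir while removing matching AdhereTech patients. The text does not settle this, because the first clause can be applied to both arms. The documents also give no SD of change and no stopping rate from which to size a bias.

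**Conclusion.** The feasibility comparison is not like for like, and this follows from the plan's wording without any assumed rate. Its consequence is modest if bottle stopping among retained patients is 3% to 5% and substantial at 10% to 20%, on the assumptions of equal 90% retention and 35 per arm. It acts in one direction only, against the bottle.

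Objective 2 lacks the analysis that its wording calls for. That analysis would have moderate precision, and less if enrollment stops near 40.

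The per-protocol point is a missing definition. A reader might infer a demonstrated bias towards the bottle, but the documents do not support that. All three points concern secondary analyses; the primary intention-to-treat comparison uses none of these definitions. The changes should be made before the secondary data are analysed.

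**What to change.** - **Feasibility:** compare completion of 12-week follow-up in both arms as a risk difference with 95% CI. Report bottle-intervention completion, with a CI and reasons for stopping, descriptively in the AdhereTech arm. The cost is that bottle stopping loses its p-value.
- **Objective 2:** keep the between-arm tests. Add Spearman correlations, with 95% CI, of TFV-DP with plasma tenofovir and with self-report at week 0, at week 12 and for change, the last two adjusted for arm. Interpret them in light of the different windows: the Background describes "plasma tenofovir levels that estimate short-term adherence over 1-3 days", against 12 weeks for the blood spot. A low correlation alone would not show that either marker is poor. All three measures are collected at weeks 0 and 12, and the Table 1 footnote already commits to the plasma assays at those weeks, so no new visits, samples or assays are needed.
- **Per-protocol (minor):** define completion in both arms and apply the listed exclusions to both. Treat the result as supportive, because exclusions made after randomization, including those for regimen change, can select on outcome.
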